### Abstract:

**Backgrounds**: this study, as the second part, aims to detect the correlation between the coronary artery stenosis, Canadian Cardiovascular Society(CCS) angina pectoris classification and the differential functional status of acupoints in distinguishing the severity of chronic stable angina.

**Methods:** We apply the cross-sectional study design to carry out the exemplary research in the aspects of disease diagnosis, in order to confirm the hypothesis "acupoint sensitization is associated with the severity of angina pectoris, and can contribute to the diagnosis of stable angina pectoris".

**Discussion**: This project will enrich the basic theory of TCM with a clear point of different functional acupoint status in the diagnosis of stable angina, which will offer important examples for the clinical application in disease diagnosis.

Keywords: Study protocol, diagnostic trial, stable angina pectoris

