# 2.1 Study population

Eligible stable angina pectoris patients should match the inclusion criteria and the exclusion criteria. Inclusion criteria: participants will be included if they fulfill the following criteria:1)patients meet the diagnostic criteria of ACC/AHA angina pectoris of coronary heart disease; 2)35≤age ≤80 years, male or female; 3) the onset of

angina pectoris ≥3 months and the frequency of angina attack≥twice a week; 4)

patients agree to do coronary angiography examination and signed the informed consent. Exclusion criteria: patients with any of the following conditions will be excluded:1)People with mental disabilities and intelligent obstacle;2) Patients who can't accomplish the detection of acupoint sensitization;3)Patients with allergic condition, especially the contrast media;4) Patients with acute myocardial infarction, unstable angina, during arrhythmia and serious diseases which can affect the blood supply of myocardial;5) Skin or peripheral nerve paresthesia, pain or the detect area of skin ulcerate;6) pregnant or lactating women;7) Patients who undergoing other clinical trials.

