#### 2.5 Recruitment procedures

The following scheme will be used to recruit participants with angina pectoris. Patients visiting the outpatient clinics and inpatient department in the department of Cardiology of the West China Hospital in Sichuan university will be informed by the cardiologist of the present trial. Research assistants will continue the enrollment process by screening eligible participants according to the inclusion/exclusion criteria. Participants will be included only if they meet the inclusion criteria and provide written informed consent indicating that they agree to every procedure of the trial and join in the trial willingly.

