# 2.6 Sample size calculation

According to the diagnostic test sample size, ensuring the accuracy in the prediction, sensitivity is set 80% and specificity is 60%,  $\alpha = 0.05$ , the difference between the samples and the overall is  $\delta = 0.10$ . Considering a 15% dropout, 183 participants will be included in this trial finally.

$$n = Z_a^2 \times p \times (1-p)/\delta^2, (\alpha = 0.05, \delta = 0.1)$$

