### 3. Statistical analysis

Analysis were conducted to explore relationships between the degree of acupoint sensitization, the degree of coronary artery stenosis and CCS angina pectoris classification by SPSS20.0 software. For the collected data, the mechanical pain threshold of acupoint sensitization collected by Von Frey electronic measuring instrument and the degree of coronary angiography are continuous quantitative data. The grade of Canadian angina is qualitative data and specific correlation analysis method will be choose based on the type and distribution of collected data. Diagnostic value will be further analyzed in the final step.

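### The plan sets out to confirm a role in diagnosing stable angina but enrols only patients who already have it, so that half of the hypothesis cannot be tested

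*Protocol*

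**What the plan says.** The Abstract states the hypothesis that the design is meant to confirm. It has two separate claims: that sensitization is associated with the severity of angina, and that it "can contribute to the diagnosis of stable angina pectoris". The abstract's discussion repeats the second, promising a result on "different functional acupoint status in the diagnosis of stable angina".

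The first inclusion criterion in Section 2.1 is that "patients meet the diagnostic criteria of ACC/AHA angina pectoris of coronary heart disease". Section 2.5 confirms the source: "The following scheme will be used to recruit participants with angina pectoris". Section 2 describes a single group assessed once. No section provides for healthy people, people without angina, or people with suspected but unconfirmed angina.

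Section 2.6 sizes the study as a diagnostic test: "sensitivity is set 80% and specificity is 60" per cent, with alpha 0.05 and delta 0.10. It ends: "Considering a 15% dropout, 183 participants will be included in this trial finally". The condition that these two figures refer to is not named. Section 3 plans correlations among sensitization, stenosis and CCS class, and adds: "Diagnostic value will be further analyzed in the final step". No target condition is given there either.

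**The concern.** A claim that a test helps to diagnose a condition needs people with and people without that condition. Here everyone has stable angina at entry. With that target:

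- Specificity has a denominator of zero, and the AUC is undefined.
- The positive predictive value is 1 and the negative predictive value is 0, however the test behaves.
- Sensitivity can be estimated, but it cannot show discrimination: a test that is positive in everyone has 100% sensitivity.

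The data can therefore support a statement about severity among angina patients, but none about telling angina from non-angina. The risk is that a positive correlation with severity is reported as evidence of diagnostic value for stable angina, because the hypothesis and the abstract's discussion are already worded that way. No analysis after enrolment can repair this.

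**Working it through.** **Inputs (Protocol, Section 2.6).** Sensitivity 0.80, specificity 0.60, two-sided alpha 0.05 (Z = 1.96), delta 0.10, dropout 15%, total 183. Formula: n = Z² × p × (1 − p) / delta².

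**Reproducing the 183.**

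- Sensitivity: 1.96² × 0.8 × 0.2 / 0.01 = 61.5, rounded up to 62 reference-positives.
- Specificity: 1.96² × 0.6 × 0.4 / 0.01 = 92.2, rounded up to 93 reference-negatives.
- Sum: 62 + 93 = 155 evaluable.
- Dropout: 155 / 0.85 = 182.4, rounded up to 183, which matches. (155 × 1.15 = 178.3 does not.)

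The larger part of the stated sample size, 93 of 155, thus consists of people without the target condition.

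**If the target is stable angina.** All 155 evaluable patients are positive and none is negative, against 93 implied. Only sensitivity can be estimated, with half-width 1.96 × √(0.16/155) = 0.063, or 6.3 points.

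**If the target is angiographic stenosis within angina patients.** The Protocol gives no prevalence, so the values below are assumptions. With 155 evaluable, the half-widths are 1.96 × √(0.16/positives) for sensitivity and 1.96 × √(0.24/negatives) for specificity. The enrolment that keeps ±0.10 on both is max(62/prevalence, 93/(1 − prevalence)) / 0.85, rounded up.

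| Assumed prevalence | Positives / negatives | Sensitivity half-width (points) | Specificity half-width (points) | Enrolment for ±0.10 on both |
|---|---|---|---|---|
| 30% | 46.5 / 108.5 | 11.5 | 9.2 | 244 |
| 40% | 62 / 93 | 10.0 | 10.0 | 183 |
| 50% | 78 / 77 | 8.9 | 10.9 | 219 |
| 70% | 108 / 47 | 7.5 | 14.0 | 365 |
| 90% | 140 / 15 | 6.6 | 24.8 | 1095 |

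Counts are rounded to whole patients except in the 30% row. On this reading, 183 delivers the planned precision on both measures only near 40%.

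**Severity half.** Stenosis and CCS class can vary among angina patients, so no comparator is needed. With 155 evaluable and 80% power (the power is an assumption), the detectable correlation by Fisher's z is tanh((1.96 + 0.84)/√152) = 0.22.

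**The case against.** The strongest reply is that diagnosis is used loosely. Section 1 calls angiography the gold standard for lesion severity, the stated aim is to distinguish severity, and the operational sections plan only stenosis, CCS class and sensitization. On that reading the fault is one badly worded phrase, and the figure of 0 negatives against 93 belongs to a reading that the rest of the Protocol does not follow. It is true that Sections 2 and 3 describe a severity study. But the hypothesis names diagnosis of stable angina separately from severity, and the looser reading still leaves ±0.10 on both measures resting on an unstated prevalence of about 40%.

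A second reply is that the SAP, which is not at hand, may define the target and its cut-off. It may, but it cannot supply participants whom the eligibility criteria exclude.

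A third is that this is the second part of a larger project, so another part may have controls, and the discussion sentence may refer to the whole. That is possible for the discussion sentence. The hypothesis, however, is assigned to this design, and no pooling with another part is described.

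Two points stand. The prevalences are illustrations, so the loss of precision on the stenosis reading runs from trivial (10.9 against 10.0 points at 50%) to large (24.8 at 90%). And 80%/60% can be tied to only one condition, so a claim to discriminate CCS class would have no planned precision behind it.

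**Conclusion.** The concern holds and should be corrected before recruitment. The claim about diagnosing stable angina cannot be tested, because no participant is free of the condition. For that target the design yields 0 of the 93 reference-negatives contained in its own sample size, and only a sensitivity (about ±6.3 points) can be estimated. This rests on the Protocol's text and arithmetic alone.

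The consequence for precision on the stenosis reading is conditional on prevalence, which the Protocol does not state. The severity half is unaffected by this flaw; that is not a judgement on any other aspect of the severity analysis.

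**What to change.** 1. Limit the hypothesis and the abstract's discussion to patients with established stable angina: sensitization is associated with, and discriminates, angiographic stenosis severity and CCS class. Delete the claim about diagnosing stable angina.
2. In Section 2.6, tie the 80%/60% to one binary angiographic reference condition, fixed by the sponsor before the first patient, and state its assumed prevalence. Confine the planned accuracy figures to that condition.
3. Then either restate the precision that 183 enrolled (about 155 evaluable) gives at that prevalence, or recalculate the sample size if ±0.10 is to be kept for both measures.

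The cost is wording, a narrower claim and possibly a less favourable stated precision. No control group or extra procedure is needed, and the trial status section says that nobody has yet been recruited. Enrolment changes only if ±0.10 on both measures is kept at a prevalence away from 40%, at the numbers in the table above.

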# 1. Background

Stable angina pectoris (AP) is the result of myocardial ischemia, typified by the clinical symptoms discomfort in the chest, jaw, shoulder, back, or arms, typically provoked by physical exertion or emotional stress and relieved by rest or nitroglycerin[1]. Despite the multiple medical and interventional technologies that have been developed to reduce myocardial ischemia, the ischemic heart disease was still be the top causes of death according to the released World Health Organization (WHO) report in 2004 and the updated data published in *the New England journal medicine* 2013[2-4].

Compared to the traditional Chinese medicine (TCM) syndrome, the invasive coronary angiography(ICA) is considered the "gold standard" by providing a more accurate assessment of lesion severity than visual assessment in patients with suspected coronary artery disease (CAD), especially with high prevalent baseline cardiac risk factors[5]. A few studies have proved that there were relationships between TCM and coronary artery lesion. Historically, acupoint is described and understood with the state according to the core viewpoint and theory of The Inner Canon of Huangdi or Yellow Emperor's Inner Canon. When the human body has disease, acupoints on the body surface may be sensitized with various types of sensitization, and acupoint heat-sensitization is a type of acupoint sensitization. This sensitized acupoint can not only reflect the pathological phenomenon of the diseases but also can distinguish the severity of the disease effectively.

But, there was no study to explore the correlation between the coronary artery stenosis and the acupoint sensitization. Thus, our study is designed to explore the correlation between the coronary artery lesions, Canadian Cardiovascular

Society(CCS) angina pectoris classification and the acupoint sensitization, which can ensure the degree of acupoint sensitization in distinguishing the severity of the disease.

#### 2. Methods

This part adopts the "single entry" cross-sectional study design. After the eligible patients recruited in group, the coronary artery stenosis will be evaluated through coronary angiography and the Canadian Cardiovascular Society(CCS) angina pectoris classification will also be evaluated at the same time. The degree of acupoint sensitization will be tested by the electronic Von Frey instrument by one professional acupuncturist.

# 2.1 Study population

Eligible stable angina pectoris patients should match the inclusion criteria and the exclusion criteria. Inclusion criteria: participants will be included if they fulfill the following criteria:1)patients meet the diagnostic criteria of ACC/AHA angina pectoris of coronary heart disease; 2)35≤age ≤80 years, male or female; 3) the onset of

angina pectoris ≥3 months and the frequency of angina attack≥twice a week; 4)

patients agree to do coronary angiography examination and signed the informed consent. Exclusion criteria: patients with any of the following conditions will be excluded:1)People with mental disabilities and intelligent obstacle;2) Patients who can't accomplish the detection of acupoint sensitization;3)Patients with allergic condition, especially the contrast media;4) Patients with acute myocardial infarction, unstable angina, during arrhythmia and serious diseases which can affect the blood supply of myocardial;5) Skin or peripheral nerve paresthesia, pain or the detect area of skin ulcerate;6) pregnant or lactating women;7) Patients who undergoing other clinical trials.

# 2.2 Detection of acupoint sensitization

Theoretically, the higher readings of the Von Frey electronic measuring instrument, the higher the degree of acupoint sensitization. First of all, in order to ensure the privacy of the participants, an independent sensitizing detection room will be set. Meanwhile, there must be a nurse or other medical staff when the female subjects in sensitization detection operation. Secondly, the participants pose the right position, double lower limbs stretch the knee, testers press each region with finger and proper strength in total 12 acupoints, including Shenmen, Yinxi, Shaohao, Jiquan, Neiguan, Ximen, Quze, Danzhong, Juque, Jueyinshu, Xinshu, Dushu. Researchers detect the sensitization of acupoints by using Von Frey electronic measuring pain instrument. Every acupoint will be tested for 2 times, and if the mean value is higher than 15, the third test will be conducted.

All the collected data will be documented in the case report form(CRF). At the same time, the data will be saved in the computer folder which established beforehand.

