#### 2.8 Benefits and risks

This study is a single entry, cross-sectional and diagnostic studies. During this research, patients did not receive any therapeutic interventions, but stick to the original angina treatment plan. The main detection of acupoint sensitization concerned with stable angina pectoris by the VonFrey electronic measuring instrument: just put the instrument probe at the acupoint sensitization on the surface of the skin and record the data displayed in the instrument. In the process of operation, the sponsor will shoulder the economic burden caused by the occurrence of adverse events related to this study. Besides, the cost in the following examination may reduce considerably. In order to protect patient privacy, all the data are shrouded in secrecy, all relevant researchers must sign a confidentiality agreement before access to the data.

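### The protocol says a higher Von Frey reading means more sensitization, yet names that reading a pain threshold, for which lower means more sensitized

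*Protocol*

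**What the plan says.** - **Protocol, Section 2 (Methods)** makes the electronic Von Frey device the measure of the degree of sensitization: "The degree of acupoint sensitization will be tested by the electronic Von Frey instrument by one professional acupuncturist". Section 2.2 also mentions pressing with the finger, but plans no measurement from it.
- **Protocol, Section 2.2** gives the only directional statement in the document: "Theoretically, the higher readings of the Von Frey electronic measuring instrument, the higher the degree of acupoint sensitization". It also describes the device as one that measures pain: "Researchers detect the sensitization of acupoints by using Von Frey electronic measuring pain instrument". A third test is required when the mean of two readings exceeds 15; neither a unit nor a reason is given.
- **Protocol, Section 2.8** describes the operation as placing the probe on the skin and then to "record the data displayed in the instrument". No conversion of the displayed value is mentioned.
- **Protocol, Section 3** names the analysis variable as "the mechanical pain threshold of acupoint sensitization collected by Von Frey electronic measuring instrument" and treats it as continuous. It states no direction, cut-off or test-positive rule.
- **Protocol, Abstract and Section 1** set out what the variable is for. The hypothesis is that "acupoint sensitization is associated with the severity of angina pectoris", and the rationale is "When the human body has disease, acupoints on the body surface may be sensitized".

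**The concern.** Sections 2.2 and 3 describe the same reading from the same instrument. Section 2.2 says it rises with sensitization. Section 3 gives it a name whose ordinary meaning implies that it falls with sensitization. If the reading is a threshold, the Section 2.2 sentence is backwards. If it is something else, Section 3 misnames the analysis variable.

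The main conclusion depends on this direction. Suppose thresholds fall as stenosis or CCS class rises, which is what the rationale predicts if the reading is a threshold. An analyst who follows Section 2.2 would report that sensitization falls with severity, the reverse of what the data show. If a high reading were also taken as test-positive, the least sensitized patients would be called positive. The p-value would give no warning, because it does not change with the sign.

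**Working it through.** **1. The texts side by side**

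| Source | Statement about the reading | Direction |
|---|---|---|
| Section 2.2 | higher reading, more sensitization | stated: up |
| Section 3 | the reading is a mechanical pain threshold | implied by the term: down |
| Section 2.8 | the displayed value is recorded | none; no transformation |
| Section 2.2, retest at a mean above 15 | third test at high readings only | none; no unit or purpose |

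Nothing in the last two rows reconciles the first two. With no unit given, the document cannot show which sentence is wrong.

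**2. The plan's own sample size (Section 2.6)**

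Inputs: sensitivity 0.80, specificity 0.60, alpha 0.05 (taken as two-sided, Z = 1.96), delta 0.10, dropout 15%. Formula: n = Z² × p × (1 − p) / delta².

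- Sensitivity: 1.96² × 0.80 × 0.20 / 0.10² = 61.5, rounded up to 62.
- Specificity: 1.96² × 0.60 × 0.40 / 0.10² = 92.2, rounded up to 93.
- Sum: 62 + 93 = 155. With dropout: 155 / 0.85 = 182.4, rounded up to 183.

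The stated 183 is reproduced. The direction of the scale does not enter the formula.

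**3. Effect on a correlation**

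The protocol gives no expected correlation, so r is assumed. With r = 0.30 and n = 155:

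- t = 0.30 × √153 / √(1 − 0.09) = 3.89, p = 0.00015.
- Fisher 95% CI: tanh(0.3095 ± 1.96 / √152) = 0.15 to 0.44.
- Reversed: r = −0.30, CI −0.44 to −0.15, the same p.

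Over an assumed range of |r| the p-value is again the same for either sign: 0.013 at 0.20 and 2.5 × 10⁻⁷ at 0.40.

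**4. Effect on diagnostic accuracy**

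This takes a cut-off that achieves the planning values and reads that same cut-off from the wrong side.

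- Sensitivity: 1 − 0.80 = 0.20. Specificity: 1 − 0.60 = 0.40.
- Youden index: 0.80 + 0.60 − 1 = +0.40 becomes 0.20 + 0.40 − 1 = −0.40.
- Positive likelihood ratio: 0.80 / 0.40 = 2.0 becomes 0.20 / 0.60 = 0.33.
- AUC, under an assumed equal-variance binormal model: d = z(0.80) + z(0.60) = 1.095; AUC = Φ(1.095 / √2) = 0.78, which becomes 1 − 0.78 = 0.22.

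**The case against.** The strongest reply is that only one direction is written down. Section 3 states none; that a lower threshold means more sensitization is an inference, and the protocol speaks of several types of sensitization without defining it as a lowered pain threshold. The Section 2.2 sentence is framed as theory and is not tied to any score or cut-off, and the hypothesis attaches no sign to the reading. The harm therefore arises only if someone applies that sentence to raw thresholds, and an AUC below 0.5 would probably expose the reversal.

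Part of this stands. Nothing has been mis-scored yet, and an alert analyst could correct the sign. The illustrative figures are conditional: the correlations and the binormal model are assumptions, and the 20% and 40% require one fixed cut-off read from the wrong side, whereas a cut-off chosen from the data would generally give other values.

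The reply does not remove the conflict. The inference rests on what a pain threshold means and needs no outside figure. The Section 2.2 sentence is the only guidance on direction that a reader has. Nor is this a detail that may wait for a statistical analysis plan: the protocol has already fixed a direction, and it is at odds with the name of the analysis variable.

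The retest rule at 15 also deserves attention. It adds a measurement at high readings only, and whether it relies on the Section 2.2 direction cannot be told.

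**Conclusion.** The concern holds, and the text must be corrected before recruitment. Sections 2.2 and 3 cannot both be right, and the document does not show which one is wrong. The conclusion rests on the ordinary meaning of pain threshold.

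If the Section 2.2 rule is applied to raw thresholds, the reported association between sensitization and severity changes from r to −r. If a high reading is also taken as positive at an unchanged cut-off, sensitivity and specificity become their complements. The size of r, its p-value and the planned 183 patients are unaffected. The contradictory wording does not itself alter the values recorded from the instrument, but the role of the retest rule remains open.

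**What to change.** In Section 2.2, state what the instrument reading is, its unit and which direction means more sensitized, and make Section 3 agree.

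- If the reading is a pain threshold, replace the Section 2.2 sentence with one saying that a lower threshold means a higher degree of sensitization.
- If it is not a threshold, keep the stated direction and correct the term in Section 3.

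Use that single direction when interpreting every correlation and for any test-positive rule. Check the retest rule at 15 against the same definition, and give its unit and purpose.

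The cost is one sentence or one term, plus the unit and a check of the retest rule. It requires no additional patients or visits. The trial status section says that nobody has been recruited, so the direction can be settled before any data exist and cannot appear to have been chosen to suit the results.

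### Does taking a third Von Frey reading only when the first two average above 15 distort the index measurement?

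*Protocol*

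**What the plan says.** Section 2.2 names 12 acupoints to be tested in each patient and sets the number of readings: "Every acupoint will be tested for 2 times, and if the mean value is higher than 15, the third test will be conducted". It gives no unit for 15 and no reason for it, and does not say how two or three readings become one value.

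Section 3 treats the result as continuous: "the mechanical pain threshold of acupoint sensitization collected by Von Frey electronic measuring instrument and the degree of coronary angiography are continuous quantitative data". It is to be related to stenosis and to CCS class, and then: "Diagnostic value will be further analyzed in the final step".

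Section 2.6 bases the sample size on sensitivity and specificity alone: "Considering a 15% dropout, 183 participants will be included in this trial finally". The number of readings plays no part in it.

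**The concern.** A replicate rule triggered by the level of the measurement, rather than by disagreement between replicates, invites suspicion for two reasons.

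- **Uneven precision.** Points above 15 would rest on three readings and points below on two, so measurement error would differ across the scale.
- **Selective correction.** When the first two readings are high by chance, a third pulls the mean back. When they are low by chance, nothing does. Averages near 15 would then be too low.

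This is the study's index measurement. If the distortion were sizeable, it would weaken the correlation with stenosis and CCS class and carry over into the assessment of diagnostic value. Giving every point the same number of readings would avoid it and would take one sentence.

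**Working it through.** **The plan's own figure.** With n = z²p(1−p)/δ², z = 1.96 (two-sided) and δ = 0.10 from section 2.6:

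- sensitivity 0.80: 61.46, rounded up to 62
- specificity 0.60: 92.20, rounded up to 93
- sum 155; 155/(1 − 0.15) = 182.4, rounded up to 183

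The stated 183 reproduces and does not depend on the number of readings.

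**Size of the local effect, if the third reading is averaged in.** Let w be the SD of one reading, assumed constant, and T the true value. The mean of two readings has error SD w/√2 = 0.707w; the mean of three has w/√3 = 0.577w. The bias of the final mean is

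−(1/3)(w/√2) φ((15 − T)/(w/√2)).

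At T = 15 this is −(1/3)(0.7071)(0.3989)w = −0.094w. It is −0.073w at 0.5w from 15, −0.035w at 1w, −0.010w at 1.5w and under 0.002w at 2w. If the third reading is not analysed, there is neither bias nor a difference in the number of readings.

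**Effect on the correlation.** The protocol gives no unit, level or SD, so these inputs are assumptions: SD of true values 5, w = 3 or 5, true correlation 0.30, mean reading 12 or 15. Let q be the share of points that trigger a third reading. Five schemes can be compared:

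- the stated rule, third reading averaged in (integrated over the normal distribution of T)
- a third reading given at random to the same share q: error variance w²[q/3 + (1 − q)/2]
- an equal number of readings for all with the same total presses (hypothetical, 2 + q per point): w²/(2 + q)
- two for all: w²/2
- three for all: w²/3

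For the last four, the observed correlation is 0.30 × √[25/(25 + error variance)].

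| w | mean | q | stated rule | random third | equal, same total | two for all | three for all |
|---|---|---|---|---|---|---|---|
| 3 | 12 | 0.290 | 0.2783 | 0.2782 | 0.2789 | 0.2762 | 0.2835 |
| 3 | 15 | 0.500 | 0.2798 | 0.2798 | 0.2805 | 0.2762 | 0.2835 |
| 5 | 12 | 0.312 | 0.2495 | 0.2493 | 0.2507 | 0.2449 | 0.2598 |
| 5 | 15 | 0.500 | 0.2523 | 0.2521 | 0.2536 | 0.2449 | 0.2598 |

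Worked case (w = 5, mean 12, random third): 25 × (0.312/3 + 0.688/2) = 11.20; 0.30 × √(25/36.20) = 0.2493.

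With 155 analysed, the standard error of a correlation of 0.30 is (1 − 0.09)/√154 = 0.073. Against it:

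- Stated rule versus three for all: 0.004 to 0.010 lower, about 5 to 14% of one standard error.
- Stated rule versus random third: a difference of at most 0.0003, under 0.5% of one standard error. This comparison isolates dependence on the value. In the four cases shown the rule is, if anything, marginally ahead.
- Stated rule versus equal readings with the same total: 0.0006 to 0.0012 lower, under 2% of one standard error.
- Stated rule versus two for all: 0.002 to 0.007 higher.

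**Effect on discrimination.** In a separate simulation (true correlation 0.5, w 2 to 5, means 12 to 25), the area under the ROC curve under the rule was at most about 0.009 below three for all and never below two for all.

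**Cost of three for all.** At most 12 more presses per patient (24 to 36). Against the stated rule it is 12 × (1 − q): 6 at mean 15 and 8.3 to 8.5 at mean 12. Each press adds some exposure to the local skin effects listed in section 2.9.

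**The case for a change.** The best case for raising the point is that the number of readings is a matter of data collection, fixed in the protocol. A statistical analysis plan can choose to analyse only the first two readings, but it cannot supply third readings that were never taken. The trigger is tied to level, so it does not work as a repeatability check. No benefit of the rule is documented, recruitment has not begun, and a change would be cheap.

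Much of this stands as description. The dependence on the value is real, and the bias near 15 follows if the third reading is averaged in. But neither change repairs a shown fault. Analysing the first two everywhere removes the bias yet lowers the correlation, and an analysis plan could adopt it without a protocol change. Three for all gains precision because it presses more often, as any added replicate would.

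The uneven precision is itself an assumption. If single-reading error were about √1.5 = 1.22 times larger above 15, the rule would roughly equalise precision. If nearly all readings exceed 15, almost every point gets three readings and the effect disappears.

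The local bias would deserve more attention if 15 were a diagnostic cut-off. The protocol does not present it as one.

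A separate matter should not be used to support this one: section 2.2 says "the higher readings of the Von Frey electronic measuring instrument, the higher the degree of acupoint sensitization", while section 3 calls the reading a pain threshold. That bears on the direction of the scale, not on the number of readings.

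**Conclusion.** The concern does not hold. The rule is explicit, identical for every patient and acupoint, and inconsistent with no stated figure. Its dependence on the measured value costs essentially nothing in the correlation (at most 0.0003 in the cases examined). The larger gap of 0.004 to 0.010 against three readings for all is the price of fewer presses. A bias of up to 0.094w near 15 remains possible, but only if the third reading is averaged in, which the protocol does not say and an analysis plan not at hand may decide.

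The correlation figures rest on assumed SDs, levels and true correlations and on normal errors with constant w. The bias, in units of w, needs only normal errors and averaging. No conclusion of the study is threatened; the number of replicates is a measurement preference with a trade-off on either side.
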